3.1.3 Follow Up (Day 30)

Follow up data will be collected at 30 days following initiation of study treatment.

3.1.4 Allocation to Interventional Group

The randomization algorithm will be built into the electronic data capture system, Redcap, which will be used to collect data in the study. Once the randomization form is entered into the system and saved, the back end algorithm will run and a participant will be assigned an arm corresponding to either study device (Group A – Core warming) or standard of care (Group B – Control). Patients will undergo randomization after being enrolled into the study and prior to the placement of the core warming device. Randomization will be performed in a 1:1 fashion and maintained on the limited access, encrypted, Redcap database.

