Objectives	
Primary:
 
 • Determine the change in PaO₂/FiO₂ ratio at 0, 24, 48, and 72 hours after implementation of core warming of ventilated patients, and compare this change to patients undergoing standard care. 
Secondary:
 
 • Determine the change in viral load measured in nasopharyngeal swab by Cycle Threshold at 0, 24, 48, and 72 hours after implementation of core warming of ventilated patients, and compare this change to patients undergoing standard care. • Measure the impact of core warming on duration of mechanical ventilation. • Determine impact of core warming on patient mortality.
Number of Participants	22
Length of Participation	72 hour intervention phase; 30 day follow up

Inclusion Criteria	
 1. Patients above the age of 18 years old. 2. Patients with the diagnosis of COVID-19 requiring mechanical ventilation. 3. Patient maximum baseline temperature (within previous 12 hours) < 38.3°C. 4. Patients must have surrogate or legally authorized representative able to understand and critically review the informed consent form.
Exclusion Criteria	
 1. Patients without surrogate or legally authorized representative able to provide informed consent. 2. Patients with contraindication to core warming using an esophageal core warming device. 3. Patients known to be pregnant. 4. Patients with <40 kg of body mass. 5. Patients with DNR status. 6. Patients with acute stroke, post-cardiac arrest, or multiple sclerosis.
Investigational Device	Attune Medical esophageal heat transfer device – ensoETM. Used as indicated for patient temperature management.
Duration of administration	72 hours
Reference therapy	Standard temperature management as routine at study site
Statistical Methodology	A total of 11 patients for each group will be required to yield the necessary pilot data regarding the feasibility and effect of core warming on viral load and ventilation requirements.
Safety Evaluations	Standard adverse event monitoring (device is in widespread use for patient warming and cooling).
Data and Safety Monitoring Plan	The PI and research team will be responsible for data and safety monitoring.

This study will be conducted in full accordance with all applicable study site research policies and procedures and all applicable federal and state laws and regulations.

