3.1 General Design

This is a small scale pilot study to evaluate if core warming improves respiratory physiology of mechanically ventilated patients with COVID-19, allowing earlier weaning from ventilation, and greater overall survival. This prospective, randomized study will include 22 patients diagnosed with COVID-19, and undergoing mechanical ventilation for the treatment of respiratory failure. Patients will be randomized in a 1:1 fashion with 11 patients (Group A) randomized to undergo core warming, and the other 11 patients (Group B) serving as the control group who will not have the ensoETM device used. Patients randomized to Group A will have core warming initiated in the ICU or other clinical environment in which they are being treated after enrollment and provision of informed consent from appropriate surrogate or legally authorized representative.

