4.5 Total Number of Subjects and Sites

Recruitment will end when 22 participants are randomized.

5 Study Intervention

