7.2 Sample Size and Power Determination

Based on a prior study in patients with sepsis, a maximum temperature of 38.3°C to 39.4°C was associated with survival (aHR 0.61 [95% CI, 0.39-0.99]).[29] However, the effect of warming specific to COVID-19 patients remains uncertain, and as such, we are unable to accurately perform a power calculation for this pilot study. We believe that a total of 10 patients for each group will be required to yield the necessary pilot data to make an appropriate conclusion regarding the potential utility of core warming in reducing viral shedding, improving pulmonary physiology, reducing mechanical ventilation duration, and increasing patient survival. It is anticipated that data from this pilot study can be used for planning future larger studies.

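### Baseline P/F is left to chance in 22 patients and the primary comparison does not adjust for it; the method of generating the 1:1 sequence is also not stated

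*Combined protocol and SAP*

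**What the plan says.** Section 3.1.4 is the only description of allocation. It says: "The randomization algorithm will be built into the electronic data capture system, Redcap, which will be used to collect data in the study", and then: "Randomization will be performed in a 1:1 fashion and maintained on the limited access, encrypted, Redcap database". It does not mention simple randomization, blocks, strata, minimization or a fixed list.

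Section 3.1 describes the result as 1:1 "with 11 patients (Group A) randomized to undergo core warming, and the other 11 patients (Group B) serving as the control group". Section 4.5 ends enrolment on the total alone: "Recruitment will end when 22 participants are randomized". The Study Summary states: "A total of 11 patients for each group will be required to yield the necessary pilot data". Section 7.2 gives a different number: "We believe that a total of 10 patients for each group will be required to yield the necessary pilot data". It also says of the sample size: "we are unable to accurately perform a power calculation for this pilot study".

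On the outcome, section 3.2.1 lists the P/F ratio at 0, 24, 48 and 72 hours as the primary endpoint, while sections 2.1 and 7 refer to its change. The entry criteria in 4.1 and 4.2 set no P/F range. Section 7.3 compares continuous variables by the t test or Mann–Whitney U test and names no covariate. Section 5.2 says that physicians are not blinded to assignment.

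**The concern.** Baseline P/F is the time-zero value of the primary endpoint. Nothing in the design limits its spread or balances it between arms, and nothing in the analysis corrects for a chance difference. At 11 per arm such differences are common. The pilot is meant to inform a view on the usefulness of warming and to help plan larger studies, so an estimate shifted by a chance difference at baseline could carry into those plans.

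The second part is missing detail. The plan promises 11 and 11 but does not describe a mechanism that would produce it. The undescribed choice also matters for concealment, because the staff who treat and recruit at this single center know the earlier assignments.

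**Working it through.** **Inputs from the documents.** 22 randomized, 1:1, 11 per group (3.1, 4.5); unadjusted two-group tests (7.3); no P/F entry limits (4.1, 4.2). The documents give no SD, correlation, alpha or power. The only planned figure that can be reproduced is 2 × 11 = 22. The 10 per group in 7.2 would give 20.

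**Assumptions of this check.** Baseline P/F roughly normal, equal SDs at baseline and follow-up, and a baseline to follow-up correlation r of 0.3 to 0.7.

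**1. Arm sizes, by scheme.**
- Simple: P(11:11) = C(22,11)/2²² = 705,432/4,194,304 = 16.8%.
- Simple: P(10:12 either way) = 2 × 646,646/4,194,304 = 30.8%. So P(both arms at least 10) = 16.8% + 30.8% = 47.7% (unrounded figures).
- Fixed list of 11 and 11, or blocks of 2: 11:11 always.
- Unstratified blocks of 4: five full blocks plus two patients of a sixth, so P(11:11) = 4/6 = 66.7%, otherwise 10:12.
- Unstratified blocks of 6: three full blocks plus four patients of a fourth, so P(11:11) = 3 × 3/15 = 60%, otherwise 10:12.

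**2. Precision lost to unequal arms.** Efficiency relative to 11:11 is 4·n₁·n₂/22². At 9:13 it is 468/484 = 96.7%; at 8:14, 448/484 = 92.6%. Averaged over simple randomization it is 462/484 = 95.5%.

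**3. Chance gap in baseline P/F.** The standardized difference in means has SE √(1/n₁ + 1/n₂).
- 11:11: SE = √(2/11) = 0.426; 0.5/0.426 = 1.17; P(gap over 0.5 SD) = 24.1%.
- 10:12: SE = √(1/10 + 1/12) = 0.428; P = 24.3%.
- Simple randomization, averaged over all splits: P = 25.3%.

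The answer is therefore about 24–25% under every unstratified scheme. At 11:11, a gap over 0.75 SD occurs in 8% of trials and a gap over 1 SD in 2%.

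**4. Effect of a 0.5 SD gap on an unadjusted comparison.** If the warming arm starts higher by d = 0.5 SD and warming does nothing, the expected difference in levels is r·d and in change is (r − 1)·d.

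| r | Level | Change |
|---|---|---|
| 0.3 | +0.15 SD | −0.35 SD |
| 0.5 | +0.25 SD | −0.25 SD |
| 0.7 | +0.35 SD | −0.15 SD |

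**5. What adjustment gains.** The variance of the comparison, relative to an unadjusted level, is 2(1 − r) for change and 1 − r² for a baseline-adjusted analysis. For r = 0.3, 0.5 and 0.7 that is 1.4, 1.0 and 0.6 for change, against 0.91, 0.75 and 0.51 adjusted.

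**6. Predictability of a single fixed 11/11 list.** Once one arm is full, the rest are certain. The expected number of certain allocations is Σₖ 2·C(22−k, 11)/C(22,11) = 2·C(22,12)/C(22,11) = 22/12 = 1.83 patients.

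**The case against.** The plan never calls its assignment simple. A statement that 11 patients go to each group fits a restricted list at least as well, and a data-capture algorithm can run either. That stands: a reader might infer that the trial delivers 11:11 only 17% of the time, but the documents support that figure only if the unstated method is simple. Across the schemes above the range is 17% to 100%.

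The precision argument is also weak. An average efficiency of 95.5% matters little in a pilot that disclaims a power calculation.

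Unadjusted tests after randomization are valid: averaged over all possible allocations, chance imbalance creates no bias and is part of the test's stated error. That is correct, but the one trial actually run may have a sizeable gap, and the shift in its estimate is then as in step 4. P/F at 0 h is a listed measurement, so a gap could be shown by arm. It would be too strong to say that readers could not detect it. Showing a gap, however, does not correct the comparison.

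Nor do the documents say that baseline P/F is the main driver of the outcome. What they establish is that it is the endpoint's own starting value.

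Finally, stratifying 22 patients is a trade-off. Section 6.2.1 records the most recent arterial gas only if routine care produced one, and the schedule in section 6 starts PaO₂/FiO₂ recording on Day 0, so a value before randomization is not guaranteed. The documents also give no P/F distribution from which to choose a cut. This objection stands, and stratification is not required.

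**Conclusion.** The concern holds as a gap in the analysis. In about a quarter of trials of this size the arms would differ by more than 0.5 SD in baseline P/F, and section 7.3 has no adjustment for it. This does not depend on whether the unstated method is simple, a fixed list or unstratified blocks. It rests on an approximately normal baseline. The resulting shift of 0.15 to 0.35 SD rests further on equal SDs and correlations of 0.3 to 0.7, which are assumptions. Defining the endpoint as change reverses the direction of the shift and does not remove it.

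The allocation point is secondary and is one of missing detail. The documents do not support the stronger conclusion that the plan uses unrestricted assignment and will usually miss its arm sizes. They leave the method open. Even if it is simple, unequal arms cost little precision.

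**What to change.** **Main change, section 7.3.** Make the primary comparison a baseline-adjusted analysis: ANCOVA of 72 h P/F with 0 h P/F as covariate, or a repeated-measures model of the 24, 48 and 72 h values with the same covariate. State that the 0 h value is one taken before warming begins, with a matching time defined for controls. The cost is one degree of freedom and a linearity assumption. No new measurement is needed, because 0 h P/F is already part of the endpoint.

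**Secondary change, sections 3.1.4 and 3.1.** State how the sequence is generated. If blocked, vary the block size, keep it hidden from the unblinded staff, and describe the target in 3.1 as approximately 11 per arm. Avoid a single fixed 11/11 list, which leaves 1.83 final allocations certain on average. Reconcile the 10 per group in 7.2 with the 11 per group elsewhere. The cost is a few sentences and an allocation table.

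**Optional.** Stratification by P/F could be added, but it would need a guaranteed gas before randomization and a stated cut. With baseline adjustment in place it is not necessary.

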3.2 Study Endpoints

The purpose of the proposed pilot study is to determine if core warming reduces the severity of acute respiratory distress syndrome as measured by PaO₂/FiO₂ ratio 72 hours after initiation.

3.2.1 Primary Study Endpoints

The primary endpoint of this study will be:

1. PaO₂/FiO₂ ratio at 0, 24, 48, and 72 hours after initiation of core warming

3.2.2 Secondary Study Endpoints

1. Viral load measured in nasopharyngeal swab by Cycle Threshold at 0, 24, 48, and 72 hours after initiation of core warming
2. Duration of mechanical ventilation
3. Mortality

4 Study Population and Duration of Participation

All patients will have a diagnosis of COVID-19 requiring mechanical ventilation. Duration of intervention will be 72 hours. Follow-up will be to 30 days.

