5.3 Device Accountability

Core warming device accountability logs will be kept on file, will be completed on a regular basis, and will include product number, date of use, participant ID code, device damaged/destroyed and date of damage/destruction (including return date if applicable).

6 Schedule of Procedures and Data Extraction

Study Phase	Screening	Randomization/ Intervention Phase		Follow up
Study Days	Day -1to 0	Day 0	Day 1-2	Day 30
Informed Consent	X			
Review Inclusion/Exclusion Criteria	X			
Demographics	X			
Medical History/Interim History*	X			X
Physical Examination*	X		X	X
Vital Signs: Temperature, BP, HR, RR*	X	X	X	X
Height and Weight	X			
Pregnancy Test	X			
Clinical Labs	X	X	X	
Respiratory tract viral load		X	X	
Ventilator settings	X	X	X	
SOFA score	X	X	X	
Clinical Imaging (per routine)	X	X	X	
Prior/Concomitant Medications	X			X
Randomization		X		
Temperature monitoring		X	X	
PaO ₂ , FiO ₂ , parameter recording		X	X	
Adverse Event / Unanticipated Problems Assessment		X	X	X

* Interim medical history, physical exam, and vitals will be collected via chart review from routine clinical care.

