6.2 Study Visits & Data Collection

6.2.1 Screening, Enrollment, and Randomization

Study personnel will assess each subject against each inclusion and each exclusion criterion and the Investigator will determine the subject's eligibility for study participation. The principal

investigator or documented members of the research team will discuss the underlying rationale for the study, the procedures to be followed, the potential benefits and risks, and other issues mandated by the consent process with the surrogate or legally authorized representative. The participant's surrogate or legally authorized representative will be asked if they would like to participate, and if so, this will be documented using the study ICF. Determining the eligibility for each participant will require information generated during the course of routine clinical care as dictated by their attending physicians. Selected testing data will be collected in order to characterize the type, cause and severity of the patient's need for mechanical ventilation and the treatments received prior to enrollment. The data will include information from the evaluations listed below.

Once the Investigator has reviewed and signed the eligibility checklist, the research staff will enter the participant's information into the RedCap system to obtain the randomization assignment.

Data collection:

- Inclusion/Exclusion criteria review
- Study Informed Consent
- Collect Demographics (including sex/gender, race, ethnicity, and age via date of birth)
- Medical Record Review (including any history of disease, social history, physical exam findings and physicians notes)
- Review of Concurrent Medications
- Physical Exam
- Vital Signs: temperature, blood pressure, heart rate, respiration rate, height and weight
- Routine Clinical Labs/Phlebotomy such as a complete blood count (CBC) and chemistry profiles, along with most recent arterial blood gas for determination of PaO₂, if collected as routine care.
- Specific labs recorded include: sodium, potassium, creatinine, hematocrit, white blood cell count, and CRP, if collected as routine care.
- Lower respiratory tract (tracheal aspirate, sputum) viral load (cycle threshold)
- SOFA score
- Ventilator settings
- Pregnancy test for women of childbearing potential
- Randomization
- Adverse Event/Unanticipated Problem assessment and recording

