6.2.2 Post-placement

As part of routine monitoring, participants will have regularly obtained parameters (labs, vital signs, ventilator settings) recorded, as well as viral load at start and end of treatment.

- Interim medical history review
- Physical Exam
- Vital Signs: temperature, blood pressure, heart rate, respiration rate, height and weight

- Routine Clinical Labs/Phlebotomy such as a complete blood count (CBC) and chemistry profiles, along with most recent arterial blood gas for determination of PaO₂, if collected as routine care.
- Specific labs recorded include: sodium, potassium, creatinine, hematocrit, white blood cell count, and CRP, if collected as routine care.
- Lower respiratory tract (tracheal aspirate, sputum) viral load (cycle threshold)
- Ventilator settings
- Adverse Event/Unanticipated Problem assessment and recording

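### Viral load, the first secondary endpoint, is defined on a nasopharyngeal swab at four times, but Section 6.2 collects lower-tract samples and times them at the start and end of treatment.

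*Combined protocol and SAP*

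**What the plan says.** Four places define or state the endpoint, and they agree. The objectives in the Study Summary and in Section 2.2 read "Determine the change in viral load measured in nasopharyngeal swab by Cycle Threshold at 0, 24, 48, and 72 hours". The endpoint lists in Sections 3.2.2 and 7.1 read "Viral load measured in nasopharyngeal swab by Cycle Threshold at 0, 24, 48, and 72 hours after initiation of core warming".

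Three places describe what staff are to collect:

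- The schedule in Section 6 has a row "Respiratory tract viral load", marked under Day 0 and Day 1-2. It names no site.
- The lists in Sections 6.2.1 and 6.2.2 both carry the item "Lower respiratory tract (tracheal aspirate, sputum) viral load (cycle threshold").
- The opening sentence of Section 6.2.2 says routine parameters will be recorded, "as well as viral load at start and end of treatment".

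Viral load also appears in the justification for the trial's size. The Study Summary says 11 patients per group are needed to yield the "necessary pilot data regarding the feasibility and effect of core warming on viral load and ventilation requirements". Section 7.2 puts the "potential utility of core warming in reducing viral shedding" first among the conclusions sought.

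**The concern.** An endpoint can be analysed only if the procedures produce the measurement it names. Here the definition and the collection instructions name different anatomical sites. No section says that both sites are sampled, or which one supplies the endpoint.

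Two outcomes are possible. If staff work from Section 6.2, no nasopharyngeal sample is taken and the endpoint as worded is empty. If some work from the endpoint sections and others from Section 6.2, cycle thresholds from different sites enter one analysis. A within-patient change from baseline could then reflect a change of specimen as well as a change over time. The procedure lists add to this by naming two kinds of lower-tract material with no rule that a patient keeps the same one. Section 7.3 has no rule for choosing or combining specimens. A sample missed during the 72-hour window cannot be recovered later.

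**Working it through.** The plan gives no specimen count and no power calculation, so there is no figure to reproduce. The check compares every place that gives a specimen or a time for viral load.

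| Place | Specimen | Times |
|---|---|---|
| Study Summary, objectives | Nasopharyngeal swab | 0, 24, 48, 72 h |
| Section 2.2 | Nasopharyngeal swab | 0, 24, 48, 72 h |
| Section 3.2.2 | Nasopharyngeal swab | 0, 24, 48, 72 h |
| Section 7.1 | Nasopharyngeal swab | 0, 24, 48, 72 h |
| Section 6 schedule | Respiratory tract, site not given | Day 0 and Day 1-2; the next column is Day 30 |
| Section 6.2.1 | Tracheal aspirate, sputum | None stated beyond enrolment |
| Section 6.2.2 | Tracheal aspirate, sputum | Start and end of treatment |

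**Specimen.** All four endpoint and objective statements name the swab. Both procedure lists with viral load name lower-tract material, and neither names a swab. The schedule row would allow either, so it does not settle the question.

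**Timing.** The endpoint needs four times per patient. The Section 6.2.2 sentence gives two. The schedule gives Day 0 plus one or two samples on Day 1-2, that is two or three. If Day 0 is the start of treatment and sampling is daily, Days 0, 1 and 2 are 0, 24 and 48 h, and 72 h has no column. The three days can also be read as spanning the whole 72 hours, but no column is labelled by hour.

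**Planned samples.** The inputs are 22 patients (Section 4.5), 11 per arm (Section 3.1), and complete sampling, which is an assumption. Samples = patients × times.

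- Endpoint definition: 22 × 4 = 88, or 11 × 4 = 44 per arm.
- Section 6.2.2 sentence alone: 22 × 2 = 44.
- Schedule alone: 22 × 2 = 44 to 22 × 3 = 66.
- Schedule plus an end-of-treatment sample at 72 h: up to 22 × (3 + 1) = 88.
- Nasopharyngeal swabs named in the Section 6.2 lists: 0 under any reading.

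**The case against.** The timing conflict is the weaker half. Section 6.2.2 does not say that viral load is measured *only* at the two ends of treatment, and the schedule marks Day 1-2 as well. Read together, they can reach the endpoint's four times. This stands as far as it goes: the timing can be reconciled by interpretation, but no section states that interpretation.

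The no-data outcome is a worst case. It requires staff to follow Section 6.2 and disregard the endpoint sections, and the list in Section 6.2.1 is not worded as exhaustive. That is also fair. But if lower-tract samples were meant as an addition, the lists would be omitting the one sample that defines the endpoint, and that would need correcting too. Nor can staff simply fall back on routine results. The blood gas and specific laboratory items in those lists are limited to what routine care provides, whereas the viral-load item carries no such condition.

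The four endpoint statements repeat one definition, and the totals are multiples of 22 that ignore deaths, extubations and missed samples. Both points are right. The count shows how widely the wording has to be reconciled, and the totals are planned maxima.

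Finally, this is a secondary endpoint in a small pilot with no power calculation. That limits the severity, but the specimen conflict remains.

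**Conclusion.** The concern holds. On specimen the plan contradicts itself: four statements name a nasopharyngeal swab, and both procedure lists with viral load name only lower-tract material. On timing it is inconsistent: four times by the endpoint, two by the Section 6.2.2 sentence, and two to three by the schedule alone. With full sampling of 22 patients, that is 88 planned samples against 44, or 44 to 66.

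This should be fixed, although it does not threaten the main result. No primary endpoint definition, sample size or error rate changes. How much data would be lost depends on which section staff follow, and the documents do not settle that. The conclusion on specimen needs no numerical assumption. The totals assume that every patient is sampled at every time.

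**What to change.** Reconcile the Study Summary, Sections 2.2, 3.2.2 and 7.1, the Section 6 schedule, and Sections 6.2.1 and 6.2.2 to one specimen type, the same at every time within a patient, and one set of sampling times. Label the schedule columns by hour, including 72 h. The same labels would serve the PaO₂/FiO₂ row, which has the same day marks while the primary endpoint includes 72 h. Either of two options would do.

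- **Keep the endpoint.** Change the schedule and Sections 6.2.1 and 6.2.2 to a nasopharyngeal swab at 0, 24, 48 and 72 h. This is three edits, and the four endpoint statements stay as they are. The cost is up to 88 swabs that Section 6.2 does not now list.
- **Keep the Section 6.2 sampling.** Redefine the endpoint in the Study Summary and Sections 2.2, 3.2.2 and 7.1 as the change in lower respiratory tract cycle threshold from 0 to 72 h. Name tracheal aspirate or sputum, not both, and make the schedule and both lists agree. This plans 44 samples and none beyond Section 6.2, but it gives up the 24 h and 48 h values. A patient off the ventilator before 72 h may have no tracheal aspirate, so a rule for that missing value is needed.

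The first option leaves the stated endpoint intact. The second changes it, so it should be settled before the data review that Section 8.7 plans after 10 patients. Under both, the sample size stays at 22.

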2.2 Secondary Objectives

1. Determine the change in viral load measured in nasopharyngeal swab by Cycle Threshold at 0, 24, 48, and 72 hours after implementation of core warming of ventilated patients, and compare this change to patients undergoing standard care.
2. Measure the impact of core warming on duration of mechanical ventilation.
3. Determine impact of core warming on patient mortality.

3 Investigational Plan

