4.1 Inclusion Criteria

1. Patients above the age of 18 years old.
2. Patients with a diagnosis of COVID-19 on mechanical ventilation.
3. Patient maximum baseline temperature (within previous 12 hours) < 38.3°C.

4. Patients must have a surrogate or legally authorized representative able to understand and critically review the informed consent form.

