4.2 Exclusion Criteria

1. Patients without surrogate or legally authorized representative able to provide informed consent.
2. Patients with contraindication to core warming using an esophageal core warming device.
3. Patients known to be pregnant.
4. Patients with <40 kg of body mass.
5. Patients with DNR status.
6. Patients with acute stroke, post-cardiac arrest, or multiple sclerosis.

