7.3 Statistical Methods

We will utilize standard measures to report outcomes and measure differences between groups. Specifically, we will use descriptive statistics, including mean (standard deviation) and median (interquartile range). Normality will be assessed using histograms and the Kolmogorov–Smirnov test. Categorical variables will be compared using the chi-squared test or Fisher exact test. Continuous variables will be compared using the independent samples t or Mann–Whitney U test.

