7.4 Subject Population(s) for Analysis

All patients enrolled, randomized to a study arm, and completed in the study will be included for analysis.

8 Safety and Adverse Events

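### An undetected swab has no cycle threshold: patients undetectable at hour 0 can enter and add no viral-load information, and patients who clear virus after randomization lose their value because of their outcome

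*Combined protocol and SAP*

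**What the plan says.** **Entry.** Section 4.1 admits "Patients with a diagnosis of COVID-19 on mechanical ventilation", and the Study Summary has "Patients with the diagnosis of COVID-19 requiring mechanical ventilation". Neither asks for a current positive PCR, a test date, a cycle-threshold limit or a maximum time since onset. None of the six exclusions in 4.2 concerns a viral test; the last, for example, is "Patients with acute stroke, post-cardiac arrest, or multiple sclerosis".

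**Endpoint.** Sections 3.2.2 and 7.1 list "Viral load measured in nasopharyngeal swab by Cycle Threshold at 0, 24, 48, and 72 hours after initiation of core warming". The objective in 2.2 is to "Determine the change in viral load measured in nasopharyngeal swab by Cycle Threshold at 0, 24, 48, and 72 hours after implementation of core warming" and to compare this change with standard care. Section 7.2 expects the pilot to support a conclusion about viral shedding.

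**Analysis.** Section 7.3 states: "Continuous variables will be compared using the independent samples t or Mann–Whitney U test". Section 7.4 states: "All patients enrolled, randomized to a study arm, and completed in the study will be included for analysis". The plan gives no detection limit, no value for an undetected swab and no analysis set defined by detectable virus. The only missing-data text, in 9.2, concerns how forms are completed.

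**Sampling.** The endpoint is nasopharyngeal, but 6.2.1 and 6.2.2 list "Lower respiratory tract (tracheal aspirate, sputum) viral load (cycle threshold". The endpoint has four sampling times, while 6.2.2 has viral load only at the start and end of treatment. The schedule in section 6 marks it on Day 0 and Day 1–2, and the next column is Day 30.

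**The concern.** A cycle threshold exists only when the assay detects virus; a higher value means less virus, and a negative result has no value. The endpoint is therefore undefined for two kinds of patient, with different consequences.

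A patient undetectable at hour 0 has no baseline and so no change. Nothing in the plan prevents such a patient from being randomized, and each one reduces an already small comparison.

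A patient detectable at hour 0 who becomes undetected by 72 hours has a baseline but no final value. Clearance is the result the hypothesis hopes for. If it removes the patient from a test on cycle thresholds, the loss depends on the outcome and falls more heavily on whichever arm clears faster. Section 7.2 intends the data for planning larger studies, so an understated viral effect would be carried into that planning.

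**Working it through.** **The plan's own figure.** The size of 22 (11 per arm; 7.2 speaks of 10 per group) has no formula behind it. Section 7.2 says that a power calculation was not possible, so there is nothing to reproduce. The figures below show scale only.

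**1. Can an undetectable patient enter?** Yes. The criteria in 4.1 and 4.2 contain no viral test. Viral load is collected around randomization (6.2.1; Day 0 in the schedule) but does not decide entry.

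**2. Does any rule supply a value?** No. Section 7.4 includes completers but does not say what number an undetected swab carries. Section 7.3 names tests and no value.

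**3. Undetectable at hour 0: precision.** Let u be the share undetectable at hour 0. The documents give no u; 10% to 40% is an assumed range. Evaluable patients per arm = 11 × (1 − u). Power is for a two-sided 5% t-test (assumed) and an effect of 1.26 SD, the difference that 11 per arm detects with 80% power.

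| u | Per arm | Power at 1.26 SD | Difference detectable with 80% power | Chance of at least one such patient in 22, 1 − (1 − u)^22 |
|---|---|---|---|---|
| 0 | 11 | 80% | 1.26 SD | 0 |
| 10% | 9.9 | 75% | 1.33 SD | 90% |
| 20% | 8.8 | 70% | 1.43 SD | 99% |
| 40% | 6.6 | 55% | 1.69 SD | over 99% |

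Hour-0 status precedes treatment, so under randomization this loss is not systematically different between arms.

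**4. Undetected after randomization: bias.** All inputs here are assumed: hour-0 cycle threshold normal with mean 30 and SD 4; assay limit 40; rise over 72 hours of 2 cycles in controls and 5 in the warmed arm, SD 3, independent of baseline. The true difference is 5 − 2 = 3.0 cycles.

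- The 72-hour value has mean 32 (control) or 35 (warmed) and SD √(4² + 3²) = 5.
- Share above the limit: control 1 − Φ(8/5) = 5.5%; warmed 1 − Φ(5/5) = 15.9%. Among patients detectable at hour 0, simulation gives 5.0% and 15.3%.
- Mean rise among those still detected = μ − (3²/5) × φ(a)/Φ(a), with a = (40 − 72-hour mean)/5.
- Control, a = 1.6: 2 − 1.8 × 0.1109/0.9452 = 1.79.
- Warmed, a = 1.0: 5 − 1.8 × 0.2420/0.8413 = 4.48.
- Difference after dropping undetected results: 4.48 − 1.79 = 2.69, about 2.7 cycles instead of 3.0. Restricting to patients detectable at hour 0 gives 2.69 as well.

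The size depends on these inputs. The direction does not: dropping favourable results more often from the arm with more of them pulls the comparison against that arm.

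**5. Does substituting the limit repair it?** Not if change scores are then ranked. With the same illustrative limit of 40, a patient going from 38 to undetected scores 40 − 38 = 2 cycles. A patient going from 20 to 30, still positive, scores 30 − 20 = 10. The clearance ranks below the persistent positive.

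**The case against.** The strongest reply is that the plan is silent and does not order any exclusion. Section 7.3 also allows chi-squared or Fisher tests, so detected versus undetected could be compared. A Mann–Whitney test can hold tied undetected results, and 7.4 keeps completers in. This is true, and a reader might infer that the protocol tells the analyst to discard clearances; it does not. But the stated endpoint is a cycle threshold and the stated test for it is a continuous one. Neither the categorical line nor 7.4 gives an undetected swab a place in that test. Whatever is done would be chosen after the fact, by a study team that 8.6 says is not blinded.

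A reader might also infer that patients without measurable virus do enter. The documents show only that they can. They give no rate, and the remark in 3.1.2 that most patients no longer have fever at ventilation concerns fever, not virus.

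Nor do undetectable baselines bias the comparison; they cost precision. And not every undetected swab is a true clearance, since sampling may be poor or the baseline may already lie near the limit.

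Broad entry is also defensible. The primary endpoint is PaO₂/FiO₂, and the rationale in 1.2 includes immune effects as well as viral replication. The documents do not support reading this as a fault in the inclusion criteria. Finally, this is one secondary endpoint of a pilot without a power calculation, which limits how serious the point can be.

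**Conclusion.** The point holds in two parts. First, patients undetectable at hour 0 can enter and contribute nothing to the change in cycle threshold. The loss is of precision only, from 11 per arm to between 9.9 and 6.6 over an assumed 10% to 40%. Second, and more important, a t or Mann–Whitney test on cycle thresholds has no value for patients who become undetected after randomization. Losing them biases the comparison against an arm that speeds clearance. The shrinkage from 3.0 to about 2.7 cycles is an illustration on assumed values; only its direction is general, and only if undetected results are left out. The primary endpoint is untouched. The gap is worth closing because a defined rank analysis is inexpensive and better than an improvised one.

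**What to change.** 1. **Reconcile the sampling first.** Choose one specimen and one set of times, and make 2.2, 3.2.2 and 7.1 agree with the section 6 schedule, 6.2.1 and 6.2.2. A patient could be negative in one specimen and positive in the other. Take the hour-0 sample before the device is started and, in controls, at the matching time after randomization; as worded, hour 0 has no meaning for controls.
2. **Analysis set (7.1).** Define the viral-load set as randomized patients with a detectable hour-0 result in that specimen. Because this is fixed before treatment, the randomized comparison is preserved.
3. **Method (7.3).** Compare arms at 72 hours with a rank test. Every undetected result receives the best rank, tied; detected patients rank below by change in cycle threshold. Do not substitute the cycle limit and rank change scores.
4. **Recording.** Code an undetected result separately from a sample that was not taken.

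Items 2 to 4 are wording. Item 1 may alter which samples are collected, depending on which sections are followed. The price is a smaller stated n for this comparison and a rank result in place of a mean difference in cycles. The inclusion criteria need no change.
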